## Background

Autism Spectrum Disorder (ASD) refers to a range of neurodevelopmental disorders involving social impairments, communication difficulties, and restricted, repetitive, and stereotyped behaviors (2009). ASD has an enormous impact on affected families and upon society as a whole (Cidav et al. 2012; Mandell 2012; Mandell et al. 2012).

Studies have shown that the majority of individuals with ASD have problems with sleep (Richdale and Schreck 2009). Research indicates that sleep difficulty in children with ASD is more frequent than in typically developing children, or those with other forms of developmental delays (Richdale and Schreck 2009; Taylor et al. 2012). Compared with typically developing children, those with autism have a reduction in sleep time, and spend a higher percentage of that time in slow wave sleep, and a much lower percentage in rapid eye movement (REM) sleep (Buckley et al. 2010). Sleep related concerns in ASD children have been linked to behavioral difficulties and family stress (Richdale and Schreck 2009). Moreover, better sleep in these children has been associated with higher scores on measures of daily living, communication, cognition, social interaction and motor skills (Malow et al. 2006; Taylor et al. 2012).

Treatments to improve sleep could therefore have important implications for these children and their families. A consensus statement in the journal Pediatrics emphasized the need for clinical trials to improve sleep specifically for children in this population (Mindell et al. 2006). This pilot investigation will assess the combined benefit of two medicines that have each shown promise in treating sleep and behavior problems in children with autism: melatonin and donepezil.

Melatonin is a widely used neurohormone available without prescription in the United States. It plays a well-documented role in modulating sleep by helping regulate the circadian sleep-wake cycle (Tordjman et al. 2013). Recent research has identified abnormalities in melatonin physiology among individuals with ASD (Rossignol and Frye 2013). In addition, a number of small randomized clinical trials (RCT) in children with ASD have shown melatonin to be well tolerated and to increase total sleep time and decrease sleep latency (Garstang and Wallis 2006; Wasdell et al. 2008; Wirojana et al. 2009; Wright et al. 2011; Tordjman et al. 2013). One RCT in ASD found that melatonin improved daytime behavior (Wasdell et al. 2008). Studies in other populations have found that the medication also increases REM sleep percentage and REM sleep continuity (Kunz et al. 2004).

Donepezil is another promising medication in ASD. It is an acetylcholinesterase inhibitor (AChEI) initially used to treat cognitive and behavioral symptoms in Alzheimer's disease (Rogers et al. 1998; Burns et al. 1999). Donepezil and other acetylcholinesterase inhibitors have also been examined in ASD in a number of small investigations and shown to be reasonably well tolerated (Hardan and Handen 2002; Chez et al. 2003; Hertzman 2003; Chez et al. 2004; Hohnadel et al. 2007; Yoo et al. 2007; Buckley et al. 2011; Handen et al. 2011; Srivastava et al. 2011; Sahu et al. 2012), though few of those were RCT (Chez et al. 2003; Handen et al. 2011; Ghaleiha et al. 2013). The results of these small RCTs are promising with regard to the behavioral impact of this class of medications. Along with its behavioral impact, a recent line of investigation led by NIH has documented that donepezil improves sleep in young ASD children (ages 2.5-6.9 years) (Buckley et al. 2011). They found it reduced REM latency, and increased the percent of sleep spent in REM, thus helping normalize this important aspect of sleep architecture (Buckley et al. 2011).

The goal of the present exploratory investigation is to see if there is a suggestion of a large additive or synergistic effect of melatonin and donepezil given together. Individually both medications improve sleep, but appear to do so in different ways, with melatonin altering circadian rhythm and donepezil altering the characteristics of REM sleep. In this pilot investigation we will examine whether their combined effects on sleep lead to a large improvement in the behavior of children with ASD. Combined pharmacotherapy is very common in clinical practice, but is rarely studied in research (Comer et al. 2010). These two medications are both well tolerated and there is no negative drug interaction between the two. This investigation will use an RCT as well as a set of exploratory analyses to assess the combined effects of

these two medications compared to placebo in terms of behavioral and sleep measures. In addition we will collect exploratory biomarkers (e.g., digit ratio, the ratio of the lengths different fingers as a measure of the balance of sex hormones during embryonic development) to relate to the various sleep and behavioral measures. A positive signal from this study may be used to guide a follow-up study with greater numbers of study subjects and statistical power.

## Methods

### **Subjects**

#### **Inclusion Criteria:**

1. Both male and female children
2. Ages 4 to 17 1/2 years
3. Diagnosis with ASD on the basis of the clinical judgment of an autism specialist, preferably using the Autism Diagnostic Observation Schedule (ADOS) (Lord et al. 2000) or the Autism Diagnostic Interview-Revised (ADI-R) (Rutter et al. 2003).

#### **Exclusion Criteria:**

1. Abnormal EEG in the past month
2. Cardiovascular problems
3. Asthma
4. Respiratory disease
5. Peptic ulcer disease
6. Renal or hepatic dysfunction (abnormal BUN/creatinine or 2x elevated liver transaminases)
7. Urinary tract obstruction
8. Underweight (BMI < 5th percentile compared to age & sex matched population)
9. Other serious illness
10. Use of any of the following drugs that might interact with study medications (anticholinergics, systemic corticosteroids, phenobarbital, peginterferon, beta-blockers or any drug that may cause arrhythmias). Drugs that induce or inhibit CYP2D6 and CYP3A4 (enzymes important for drug metabolism) will be allowed because any effects of such medications are likely to be lost in individual variability due to genetic polymorphisms (Rahmioglu et al. 2011; Teh and Bertilsson 2012).
11. Use of medications affecting sleep with a half-life of 7 days or more. Children on medications affecting sleep with a half-life of less than 7 days (including melatonin and donepezil) are eligible if they agree to discontinue use for the duration of the trial.
12. Pregnancy and lactation

### **Recruitment**

We will send “Dear Physician” letters to Stony Brook and local physicians who see children with ASD. The physicians will inform their appropriate eligible patients and their parents/legal guardians about this study and provide them with a flyer. Flyers will also be posted at the Stony Brook Neurology clinics and Stony Brook Pediatric clinics. We will ask local autism organizations to inform their members about this study. Interested patients and their parents/legal guardians can contact the study coordinator to find out more about the study and schedule a screening visit with [name]. We will also use ResearchMatch.org, a national electronic, web-based recruitment tool. An IRB-approved study recruitment message will be sent to potential study volunteers on ResearchMatch.org.

### **Screening visit**

Parent/legal guardian and patient will meet with [name] and the study coordinator to discuss the study. If all agree to participate, the study coordinator will obtain 1) informed consent from parent/legal guardian for their participation, 2) permission from parent/legal guardian for the child’s participation. [name] will assess the child’s capacity to give assent. For patients aged 12-17.5 years old and deemed capable, a signed assent form will be obtained. For patients aged 4 to 11 years old and deemed capable, verbal assent will be obtained (written if capable). For patients that are not deemed capable of giving assent, only parental consent will be obtained. If patient does not have relevant blood work in the past month, venipuncture and blood tests are needed to determine renal/hepatic dysfunction. For female patients who have menses, urine will be collected for an over-the counter pregnancy test. By signing the consent

and assent forms, female patients agree to avoid any risk of conception during the study. If any patient becomes pregnant during the study, she will have to withdraw from the study immediately. Parents/legal guardians are health care proxies of their autistic child until 18 years old, thus they will have access to their child's medical information, including results of the pregnancy test. Parent/legal guardian will be notified by phone if the patient is still eligible for the study and if they are still interested in participation. If they are, a baseline visit will be scheduled.

### Study Design

**Table 1 – Study design and medication dosage (mg)**

Week			Run-In (V0-V1)	Phase 1 (V1-V2)					Phase 2 (V2-V3)					Wash- Out (V3-V4)	
				1 - 5	6	7	8	9	10	11	12	13	14	15	
Group A	Younger*	Donepezil	P	1.25	2.5	2.5	2.5	2.5	2.5	1.25	2.5	2.5	2.5	2.5	
		Melatonin	P	3	3	3	3	3	3	3	3	3	3	3	
	Older	Donepezil	P	2.5	5.0	5.0	5.0	5.0	5.0	2.5	5.0	5.0	5.0	5.0	
		Melatonin	P	3	3	3	3	3	3	3	3	3	3	3	
Group B	Younger*	Donepezil	P	P	P	P	P	P	P	1.25	2.5	2.5	2.5	2.5	
		Melatonin	P	P	P	P	P	P	P	3	3	3	3	3	
	Older	Donepezil	P	P	P	P	P	P	P	2.5	5.0	5.0	5.0	5.0	
		Melatonin	P	P	P	P	P	P	P	3	3	3	3	3	

Key: \* Younger = children below 12 years of age or 80 lbs. weight, who start and end at a lower dose of donepezil, than the other Older children; P = Placebo

**Table 2 – Visit procedures**

Visit no.	Person in charge	Screening	Baseline (V0)	V1	V2	V3	V4
Study weeks		/	0	5	10	15	17 – 27
Incl/excl criteria*	[name]	X					
Pregnancy test (if applicable)**	CRC nurse	X					
Informed consent and assent	Study coordinator	X					
Aberrant Behavior Checklist	Parent		X	X	X	X	X
Child's Sleep Habits Questionnaire	Parent		X	X	X	X	X
Parent Global Impressions	Parent		X	X	X	X	X
Prenatal, developmental, neurological history	[name]		X				
Neurological exam	[name]		X	X	X	X	X
Clinical Global Impressions	[name]		X	X	X	X	X
Adverse event monitoring	[name]			X	X	X	X
Head circumference	CRC nurse		X				
D2/D4 finger length ratio	CRC nurse		X				
Dispense study drug	[name]		X	X	X		
Sleep hygiene education	[name]		X				
Study drug accountability	Study coordinator			X	X	X	

\*Includes renal/hepatic function test if blood work was not done within the past month

\*\* For female patients who have started menses

Patients will meet with [name] for 5 visits (baseline, follow up visit 1-4) every 5 weeks:

**Phase 1** (between follow up visit 1 and 2) – The investigation will be conducted in 2 Phases as shown in Table 1. Phase 1 will be a double-blind randomized clinical trial using a parallel group design. It will assess the combined benefit of donepezil and melatonin in Group A versus placebo in Group B over 5 weeks.

**Phase 2** (between follow up visit 2 and 3) – Phase 1 will be followed by an exploratory Phase 2 in which both groups (A & B) will be placed on the active medications for an additional 5 weeks. Phase 2 will allow us to explore whether Group A derives any additional benefit from 5 extra weeks of treatment with the active medications, and whether Group B obtains any benefit from switching from placebo to the active medications.

**Run-In Phase** (between visit 0/baseline and 1) – Phase 1 will be preceded by a Run-In Phase of 5 weeks where all subjects will receive placebo and instructions about how to improve sleep hygiene using the “Good Sleep Habits Checklist” (Durand 2014). Subjects and their families will be blinded to treatment during this phase, but investigators will not. The run-in will allow us to assess patient compliance with the study protocol. Only those who achieve compliance of at least 80% will be allowed to continue in the study and then be randomized to the two Groups. The Run-In will also allow us to control for any improvement due to better sleep hygiene. Finally, the Run-In will allow us to control for placebo effects, because the score obtained at the end of Run-In (possibly reflecting placebo effects) will be used as a baseline to which the scores at the end of each treatment phase can be compared.

**Wash-Out Phase** (between follow up visit 3 and 4) – A washout period of between 2 – 12 weeks will follow Phase 2, allowing us to explore any changes in both subject groups after active treatment has been withdrawn. The length of this period will vary in order to coincide with the next clinical visit of the patient with [name], recognizing that this data is of lower priority.

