### ***Data safety and monitoring plan***

[name], who is unaffiliated with the current study, has volunteered to serve as our data safety monitor. [name] is an associate professor in the Neurology Department here at Stony Brook who is board certified by American Board of Sleep Medicine and the American Board of Psychiatry and Neurology. [name] will periodically randomly audit the protocol documentation with the first audit occur by the enrollment of the fifth subject in order to check the quality control of the investigation early in the process, and additional audits occurring an average of every 10 subjects. Among the important goals of the audits will be to ensure that adverse events are reported, protocol amendments are filed with the IRB, inclusion/exclusion criteria are followed, and the number of patient visits do not exceed the protocol guidelines.

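### The only pregnancy test is at Screening, at least 5 weeks (Group A) or 10 weeks (Group B) before the first active dose; nobody is re-tested, and a girl whose menses start later is never tested

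*Combined protocol and SAP*

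**What the plan says.** Exclusion criterion 12 is "Pregnancy and lactation". The Screening visit section sets out the check: "For female patients who have menses, urine will be collected for an over-the counter pregnancy test". Table 2 schedules it once, in the row labelled "Pregnancy test (if applicable", under Screening, with no mark at V0 to V4, and its footnote limits it: "For female patients who have started menses". No other section schedules a repeat.

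The baseline visit is arranged later, once the family has been told by phone that the child is eligible: "If they are, a baseline visit will be scheduled". No maximum gap is given.

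The plan has other safeguards. By signing the forms, "female patients agree to avoid any risk of conception during the study". There is a withdrawal rule: "If any patient becomes pregnant during the study, she will have to withdraw from the study immediately". Table 2 schedules adverse event monitoring at V1 to V4. The Data safety and monitoring plan provides a first audit by the fifth enrolment, with "additional audits occurring an average of every 10 subjects"; checking that the eligibility criteria were followed is one of the audit goals.

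**The concern.** The plan treats exposure in pregnancy as unacceptable, because pregnancy both bars entry and ends participation. The only procedure that could detect one takes place before a placebo run-in, weeks ahead of any active drug. If the plan is followed exactly, the exclusion is enforced at entry but not when dosing starts.

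At stake is the safety of a few girls. An undetected pregnancy could be exposed to donepezil and melatonin for the whole active period. The withdrawal rule helps only once a pregnancy is known, and nothing scheduled after Screening is designed to find one.

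**Working it through.** The plan states no figure for the age of the pregnancy result, so there is none to reproduce. Its one design calculation, 91.1% power, does not depend on this point.

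**Inputs**
- Table 2: V0 = week 0, V1 = week 5, V2 = week 10, V3 = week 15; test at Screening only.
- Run-In Phase: placebo for all, V0 to V1.
- Phase 1 (V1 to V2): Group A active, Group B placebo. Phase 2 (V2 to V3): both active.
- Screening-to-V0 gap: not stated; call it L weeks, L ≥ 0.
- Drug compounding: 40 days of medication, read here as the supply per dispensing visit.

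**Age of the result = L + study week**

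| Moment | Formula | L = 0 (minimum) | L = 1 to 4 (assumed) |
|---|---|---|---|
| First active dose, Group A | L + 5 | 5 weeks | 6 to 9 weeks |
| First active dose, Group B | L + 10 | 10 weeks | 11 to 14 weeks |
| End of dosing, both groups | L + 15 | 15 weeks | 16 to 19 weeks |

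**Ceiling on exposure**, if a pregnancy is present at the first active dose and is never noticed:
- On schedule: Group A (15 − 5) × 7 = 70 days; Group B (15 − 10) × 7 = 35 days.
- If every supply is used up: Group A 2 × 40 = 80 days; Group B 40 days.

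**Does any other safeguard test before dosing?**
- Agreement to avoid conception: a promise, with no check attached.
- Withdrawal rule: acts after a pregnancy is recognised.
- Adverse event monitoring: a recurring chance to raise symptoms, but no pregnancy question or test is specified.
- Audits: review documentation.

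**Girls whose menses start after Screening.** The test depends on having menses and is offered only at Screening. With entry ages of 4 to 17½ and at least 15 weeks from Screening to the end of dosing, menses can start during the trial with no test to follow.

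**With tests at V1 and V2.** The result is current at the first active dose in both groups. On schedule it is never older than 5 × 7 = 35 days during active dosing, or 40 days if a visit is late and the whole supply is used.

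**Number of added tests** (illustrative; the plan gives no expected sex split). Two cited samples had 2 girls of 15 (13.3%) and 8 of 43 (18.6%).
- Of 60 children: 0.133 × 60 = 8.0 to 0.186 × 60 = 11.2 girls; at two tests each, about 16 to 22 if all have menses.
- If ages are spread evenly and menses start at 12: (17.5 − 12)/(17.5 − 4) = 0.407, giving 3.3 to 4.5 girls and about 7 to 9 tests.
- Upper case, from a cited general neurodevelopmental sample (42 girls of 88, 47.7%): 28.6 girls and about 57 tests if all have menses.

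**The case against.** The strongest reply is that the plan is not careless about pregnancy. A girl with menses is tested, so a pregnancy detectable at Screening is caught. She then agrees to avoid conception, must leave if she becomes pregnant, and is seen face to face about every 5 weeks, including at both visits where active drug may be dispensed. The removed consent pages may also tell families to report a missed period. The number of girls is small, and the exposure figures are ceilings that require nobody to notice for the whole active period.

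Much of this stands. It limits the likely number of cases and rules out reading the plan as having no protection. It does not supply a test: the visits are opportunities to ask, and consent wording could add reporting instructions but would not change the visit schedule.

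A reader might infer that girls in general would be dosed untested. The documents do not support that. A girl with menses at Screening has been tested once, so for her the gap is the absence of a re-test. Only a girl whose menses start later goes wholly untested.

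**Conclusion.** The point holds as a gap in the safety schedule. The single result is at least 5 weeks old (Group A) or 10 weeks old (Group B) at the first active dose, and at least 15 weeks old when dosing ends. These minimums follow from Tables 1 and 2 with no assumption beyond L ≥ 0. The longer ages, the exposure ceilings and the test counts rest on the assumptions stated with them.

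A reader might also take the 70 or 80 days as an expected exposure, or as evidence of material risk. The documents give no pregnancy rate, so neither can be said. Nor does the point touch the inference: sample size, power and alpha are unaffected. It is a cheap improvement for a small group, worth making because the plan's own exclusion is otherwise unchecked when it matters most.

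**What to change.** 1. **Table 2.** Add a mark for the existing urine test at V1 and V2, and reword the footnote to cover female patients who have started menses by that visit.
2. **Gate on the result.** Require a negative test before randomisation at V1 and before Phase 2 drug is dispensed at V2. A girl positive at V1 is never randomised, so the intention-to-treat set is unaffected.
3. **Order at V2.** Complete the outcome measures before the test. Otherwise immediate withdrawal could cost the primary Phase 1 score. Last observation carried forward would then substitute the V1 score, which is also the baseline, and so impute a change of zero.
4. **Screening visit section.** Describe the repeat tests, and state that a positive result means study drug stops at once while that visit's outcome data are kept. Without this the current withdrawal wording conflicts with step 3.

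**Cost.** Protocol wording and two over-the-counter urine tests per girl with menses: about 7 to 22 in all at a 13 to 19% female share, and about 57 in the upper case. No new visit or blood draw. Parents would see the repeat results, as they already see the Screening result, and a child may be lost before randomisation or Phase 2.

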#### **Treatment**

**Melatonin**– Melatonin is categorized by the US Food and Drug Administration (FDA) as a dietary supplement. It is widely available in the US without prescription. The dose of melatonin will be fixed at 3 mg for all participants, a level well tolerated in previous studies in this population of children (Tordjman et al. 2013). Adverse effects of melatonin have been found to be minimal to none in twenty small treatment studies in ASD (Rossignol and Frye 2013; Tordjman et al. 2013). None of the seven placebo-controlled trials of melatonin have found any increased risk of side effects (McArthur and Budden 1998; Garstang and Wallis 2006; Wasdell et al. 2008; Wirojanan et al. 2009; Wright et al. 2011; Cortesi et al. 2012; Gringras et al. 2012; Tordjman et al. 2013). Most other small studies of children with ASD taking melatonin also report no side effects (Jan et al. 1994; Horrigan and Barnhill 1997; Hayashi 2000; Jan et al. 2004; Gupta and Hutchins 2005; Giannotti et al. 2006; Galli-Carminati et al. 2009; Tordjman et al. 2013). Side effects, when noted in the other ASD melatonin studies tended to be mild and included: tiredness, daytime sleepiness, fogginess, awakening in the middle of sleep, excitement after awakening and before going to sleep, headaches, bed-wetting, and diarrhea (Ishizaki et al. 1999; Paavonen et al. 2003; Andersen et al. 2008; De Leersnyder et al. 2011; Malow et al. 2012; Tordjman et al. 2013). Dose timing is important for melatonin, and in keeping with earlier investigations (Wasdell et al. 2008; Wirojanan et al. 2009; Wright et al. 2011), parents/legal guardians will be instructed to administer it (12 ml) 30 minutes before a consistent desired bedtime. We will use supplemental melatonin in liquid form (Natrol®) as used in a previous study that obtained IND approval from the FDA for use in children with autism (Malow et al. 2012).

**Donepezil**– Donepezil, which is regulated by the FDA as a pharmaceutical drug, is also well tolerated in this population (Hardan and Handen 2002; Chez et al. 2003; Buckley et al. 2011; Handen et al. 2011; Srivastava et al. 2011). Related studies using other acetylcholinesterase inhibitors, including rivastigmine (Chez et al. 2004) and galantamine (Ghaleiha et al. 2013) have also shown that this class of medications is well tolerated in ASD children. Studies of donepezil in related pediatric clinical populations, such as fragile X (Sahu et al. 2013) and general Pervasive Developmental Disorder (Doyle et al. 2006) have found similar levels of tolerance. To maximize tolerance, the dosage will be titrated, as is commonly done in clinical trials with autistic children (Hardan and Handen 2002; Buckley et al. 2011; Handen et al. 2011). Parents/legal guardians will be instructed to administer the donepezil (1 capsule) with the melatonin, 30 minutes before a consistent desired bedtime.

**Drug compounding** –Pine Pharmaceuticals will repack the liquid melatonin from Natrol® and compound the liquid placebo. The Stony Brook Pharmacy will repack 5 mg generic donepezil into 1.25 and 2.5 mg gelatin capsules and compound the placebo in identical gelatin capsules. Patients will be given 40 days’ worth of study medication.

**Treatment Randomization** – Patients who agree to participate after they pass the screening will be assigned a study ID. After the run-in phase, study subjects will be randomly assigned to Group A or B using a computer-generated randomization plan with blocking and stratification by gender and age group (Younger: children below 12 years of age or 80 lbs. weight; Older:  $\geq$  12 years or  $\geq$  80 lbs.).

**Treatment Blinding** – The study pharmacists at Stony Brook and at Pine Pharmaceuticals will be the only individuals informed of the randomization assignments and will be responsible for labeling study drug and maintaining a master list linking patients with treatment assignments. All other research staff and participants will be masked regarding treatment assignment. Masking of active and placebo treatments will be preserved by creating liquids and capsules and containers that appear identical.

**Study Medication Accountability** – Study medication used and unused will be monitored through a drug accountability form completed at visit 1, 2, and 3.

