**Children's Sleep Habits Questionnaire (CSHQ)** – This secondary outcome measure will assess sleep, using a brief seven item questionnaire adapted from the Children's Sleep Habits Questionnaire (CSHQ) (Owens et al. 2000). This parental questionnaire assesses sleep behaviors in children (Owens et al. 2000). It has been validated in children with ASD, correlates with polysomnographic recordings, and has been used successfully in previous studies of melatonin with such children (Malow et al. 2006; Leu et al. 2011; Goldman et al. 2012). The CSHQ items chosen for this study come from the subscales found to be most often disturbed in children with autism: Sleep Duration, Sleep Onset Delay, and Night Wakings (Goldman et al. 2012).

**Clinical Global Impressions (CGI)** – The blinded treating neurologist will complete this secondary outcome in order to assess overall clinical impressions of global improvement and medication efficacy (Guy 1976).

**Parent Reported Global Impressions (PRGI)** – Modeled on the CGI, parents/legal guardians will complete this secondary outcome in order to their overall impressions of global improvement and medication efficacy.

**Biomarkers** – A variety of convenient, non-invasive, and safe biomarkers will also be collected in order to better characterize the sample and to relate to baseline behavioral and sleep measures: prenatal history (including stressors and history of exposure to selective serotonin reuptake inhibitors or terbutaline), developmental neurological history and neurological exam, D2/D4 finger length ratio (from xerox of hand), and head circumference.

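### Donepezil doubles after one week with no scheduled safety contact on active drug first; a masked telephone call before the step would close that gap cheaply

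*Combined protocol and SAP*

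**What the plan says.** All references are to the combined protocol and SAP.

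- **Dosing (Table 1).** Donepezil runs for one week at 1.25 mg (Younger) or 2.5 mg (Older), then at 2.5 mg or 5.0 mg. Group A does this in Phase 1. Both groups do it in Phase 2, because Group A returns to the low dose and steps up again. The key describes Younger children as those "who start and end at a lower dose of donepezil, than the other Older children".
- **Reason (Treatment, Donepezil).** "To maximize tolerance, the dosage will be titrated, as is commonly done in clinical trials with autistic children".
- **Visits (Table 2 and the text below it).** "Patients will meet with [name] for 5 visits (baseline, follow up visit 1-4) every 5 weeks". V1, V2 and V3 are at weeks 5, 10 and 15, and V4 is at weeks 17 to 27. Adverse event monitoring is marked at V1 to V4 and nowhere else. Of Phase 1 the text says: "It will assess the combined benefit of donepezil and melatonin in Group A versus placebo in Group B over 5 weeks".
- **Before V1 (Run-In Phase).** "Phase 1 will be preceded by a Run-In Phase of 5 weeks where all subjects will receive placebo".
- **Oversight (Data safety and monitoring plan).** The safety monitor "will periodically randomly audit the protocol documentation". One goal of the audits is that adverse events get reported.

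The available text describes no call, mid-phase visit or pre-step tolerance check, and no rule for holding or reducing donepezil.

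**The concern.** If a titration exists for tolerance, the natural moment to ask about tolerance is just before the dose goes up. Here the step happens on the calendar. A child who becomes unwell in the first week on active drug moves to twice the donepezil dose unless the family raises the problem unprompted. Some participants are as young as 4, and some may not be able to give assent, so detection rests largely on parents.

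The stake is the safety of individual children. It does not concern the validity of the Phase 1 comparison.

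**Working it through.** **Inputs**
- Dose steps: Table 1.
- Visit weeks and adverse event monitoring: Table 2.
- Phase length of 5 weeks (35 days): Table 2 and the phase descriptions. In the text as read from the PDF, Table 1's dose rows hold 12 entries against 11 week columns, so phase length is not taken from that table. The single low-dose week is the same either way.
- 60 children, 30 per group, 10% attrition, d = 0.9, 91.1% power: Analysis, Power.

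**1. Size of the step.** 2.5 / 1.25 = 2.0 (Younger); 5.0 / 2.5 = 2.0 (Older).

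**2. Last scheduled safety contact before each step**

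| Step | Preceding visit | Drug taken before that visit | Earlier contact on active drug? |
|---|---|---|---|
| Group A, Phase 1 | V1 | placebo | no |
| Group B, Phase 2 | V2 | placebo | no |
| Group A, Phase 2 | V2 | active | yes |

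Steps with no earlier contact on active drug: 30 + 30 = 60 at most. If the planned 10% attrition all falls before the step, 27 + 27 = 54. Group A's 30 Phase 2 steps are left out. These are first exposures within the trial only: Exclusion Criterion 11 lets earlier donepezil users enrol if they stop.

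**3. Time to the next contact.** 35 − 7 = 28 days.

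**4. Calls needed.** One call per child per phase, in both groups so that the procedure is the same: 60 × 2 = 120 (108 with 54 children). At an assumed 5 to 15 minutes each, 120 × 5 / 60 = 10 hours to 120 × 15 / 60 = 30 hours.

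**5. Effect on power if some capsules are stopped.** First the plan's own figure. With 27 per group and a two-sided 5% test, the normal approximation is Φ(d × √(27/2) − 1.96).
- d = 0.9: Φ(3.307 − 1.960) = Φ(1.347) = 91.1%, which reproduces the plan. Noncentral t gives 90.1%.

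Assume that a share h of the active arm is stopped and loses a share l of its effect, with the standard deviation unchanged. Then d becomes 0.9 × (1 − h × l).
- h = 5%, l = one half: d = 0.9 × 0.975 = 0.8775, power 89.7% (noncentral t 88.6%).
- h = 20%, l = all: d = 0.9 × 0.80 = 0.72, power 75.3% (noncentral t 73.8%). This is an extreme case, because melatonin continues.

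The documents give neither h nor l.

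**The case against.** **It is a design preference.** The text does not contradict itself: a fixed low-dose week can aid tolerance without a check, and the Treatment section cites several studies reporting good tolerance. This stands. A reader might infer that the titration fails its stated purpose, but the documents do not show that.

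**Families may have another route.** The consent pages are not available and may tell parents when to telephone or stop drug. The protocol also refers to a treating neurologist, so some children have ongoing care. This stands against any inference that an intolerant child has no recourse. It does not supply a scheduled contact, and neither do audits of documentation.

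**The scale of harm is unknown.** A reader might multiply an assumed 5% to 20% intolerance rate by 60 and report 3 to 12 children. No document supports such a rate. The retrospective open series of donepezil in autism, cited for tolerance and titration, reports side effects in 2 of 8 patients, but they were limited and transient and the abstract does not tie them to the first week.

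**The step may not be too fast.** The cited fragile X trial held 2.5 mg for 4 weeks before 5 mg, and a reader might infer that one week is too short for Older children. That trial is cited for tolerance in a related population, not for titration. It would support a longer low-dose period rather than a call. Another trial, which the protocol does cite for titration, used 5 and 10 mg at ages 8 to 17; its abstract gives no step length.

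**A remedy can do damage.** An automatic rule to withhold the capsule for the rest of a phase would let a Group A child who was intolerant in Phase 1 restart in Phase 2, and would not by itself require follow-up. Melatonin starts the same day and has its own reported effects, including tiredness, headaches and diarrhea, so the capsule may not be the cause. Stops would probably cluster in the active arm. Parents rate the primary outcome, and for the CGI "The blinded treating neurologist will complete this secondary outcome", so a visible stop could hint at assignment to both raters. All of this stands, and it argues for case-by-case judgement.

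**Conclusion.** The point holds as a cheap safety improvement, between optional and recommended. Up to 60 children (54 under the planned attrition) double their first in-trial donepezil dose with no scheduled safety contact on active drug beforehand, and wait 28 days for the next one. This rests on Tables 1 and 2 and the stated 5-week phases.

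The concern is stronger for Older children, who reach 5.0 mg. It is weaker for Younger children, whose final dose of 2.5 mg is the Older group's starting dose. The documents do not say how many children fall in each group. A reader might infer bias, extra dropout or a threat to the primary result; nothing in the documents supports any of these.

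**What to change.** At the end of the first week of Phase 1 and of Phase 2, before the step, the masked study coordinator telephones every family in both groups, asks the adverse event questions used at V1 to V4, and passes any positive answer to the blinded neurologist. The neurologist decides before the step whether the capsule (donepezil or placebo) continues or stops.

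If it stops:
- the coordinator calls again within about a week;
- the capsule is not restarted in Phase 2 without the neurologist's review;
- the child stays in the study, is rated at V2 and V3, and is analysed as randomised, in line with the plan's intention-to-treat principle.

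Stopping needs no new product. Keeping a child at the low dose would need up to 28 further masked low-dose capsules.

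**Cost.** About 120 short calls (10 to 30 coordinator hours on the assumed call lengths), some neurologist time and one protocol paragraph. There is no extra clinic visit, and sample size and alpha do not change. The downsides are the small masking risk when a capsule is stopped and some dilution of effect: for example, 89.7% power against the stated 91.1% if 5% are stopped and lose half their effect. A call finds only what parents report, and it leaves the 28 days after the step uncovered.
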